### 3.3. Discussion of Study Design

A single-dose, parallel design is the standard design to investigate the PK of a drug in subjects with hepatic impairment. A parallel design is required to include subjects with hepatic impairment and matched-control healthy subjects with normal hepatic function. A single dose level of LOXO-292 will be used because it has linear PK. The study will be open label because study endpoints are objective rather than subjective.

Based on the PK data from previous studies in healthy subjects, LOXO-292 has an estimated  $t_{1/2}$  of approximately 24 hours after a single dose (based on current ongoing studies: LOXO-RET-18014 and LOXO-RET-18015). Matched-control healthy subjects with normal hepatic function will be enrolled in this study to serve as a reference group for interpretation of the results. Patients with a range of hepatic impairment will be included to enhance the ability to detect and characterize the effects of hepatic function on the PK of LOXO-292. Based on nonclinical and clinical data, and the known PK profile of the compound, the duration of the treatment period is considered adequate to achieve the study objectives. Oral doses were chosen because this is the intended clinical route of administration.

Preclinical and clinical data suggest that LOXO-292 is likely to be well tolerated in healthy human subjects and may have an acceptable safety margin. However, studies in animals suggest

that the liver may be a potential target of toxicity for this drug. Liver disease can cause alterations in drug disposition, reducing the clearance of drugs eliminated by hepatic metabolism or biliary excretion and affect plasma protein binding, which in turn could influence the processes of distribution and elimination. Therefore, in this study, a cautious approach will be adopted, where the first 4 subjects from Group 2 (mild hepatic impairment subjects), the first 4 subjects from Group 3 (moderate hepatic impairment subjects), and the first 2 subjects from Group 4 (severe hepatic impairment subjects) may be dosed concurrently, followed by an interim review of the safety data – and possibly PK data – before dosing is resumed for the remaining subjects in any (all) group(s) (see [Section 8.2](#)).

### **3.4. Selection of Doses in the Study**

An oral dose has been selected for this study because this is the intended clinical route of administration. The dose of 160 mg of LOXO-292 was selected based on clinical study results and its observed PK profile. The 160-mg dose is expected to ensure sufficient quantifiable plasma concentrations of LOXO-292 for determination of systemic PK exposure. In a Phase 1/2 clinical study in cancer patients (LOXO-RET-17001), 160 mg of LOXO-292 dosed BID has been evaluated and has been selected for further testing in a larger number of cancer patients to evaluate its safety and efficacy. Current FDA guidance stipulates that a single-dose study may be satisfactory where prior evidence indicates that multiple-dose PK is accurately predicted by single-dose data for both parent drug and active metabolites (eg, when the drug and active metabolites exhibit linear and time-independent PK at the concentrations anticipated in the patients to be studied). Thus, the current study will assess the PK of a single dose of 160 mg LOXO-292 in healthy and hepatically impaired subjects.

## **4. SELECTION OF STUDY POPULATION**

Up to 8 subjects will be enrolled into each hepatic impairment treatment group to have at least 6 subjects from each group complete the study. Up to 16 subjects will be enrolled into the matched-control healthy subject group to have at least 6 healthy subjects matched to each hepatic impairment treatment group complete the study. Healthy control subjects will be matched demographically to hepatically impaired subjects as noted in [Section 3.1](#).

### **4.1. Screening Procedures**

The following screening procedures will be performed for all potential subjects at a visit conducted within 28 days of study entry (ie, prior to Check-in [Day -1]):

1. Informed consent;
2. Child-Pugh class score (subjects with hepatic impairment only);
3. Demographic data;
4. Medical history;
5. Inclusion/exclusion criteria;
6. Height, weight, and BMI;

7. Complete PE ([Section 7.2.5](#));
8. Screens for hepatitis C virus (HCV) antibody (for healthy subjects only), hepatitis B surface antigen (HBsAg), and human immunodeficiency virus (HIV) antibody ([Appendix 2](#));
9. Screen for selected drugs of abuse, including an alcohol breath test for all subjects and, for matched-control healthy subjects only, including cotinine ([Appendix 2](#));
10. Twelve-lead ECG measured after the subject has been resting in the supine position for at least 10 minutes ([Section 7.2.4](#));
11. Vital signs (including oral temperature, respiratory rate, and supine blood pressure [BP] and heart rate [HR; measured after the subject has been supine for at least 5 minutes]) ([Section 7.2.3](#));
12. Clinical laboratory evaluations ([Section 7.2.2](#); clinical chemistry panel [fasted at least 8 hours], coagulation parameters, CK, CBC, and UA; [Appendix 2](#));
13. Hemoglobin A1c test (subjects with hepatic impairment only);
14. How Do You Feel? inquiry and AE and concomitant medication evaluations ([Section 7.2.1](#));
15. Serum pregnancy test for females only ([Appendix 2](#));
16. Follicle-stimulating hormone test (for postmenopausal females only) and thyroid-stimulating hormone test ([Appendix 2](#)).

#### **4.2. Check-in Procedures (Day -1)**

At Check-in (Day -1), subjects will report to the clinical site and the following procedures will be performed:

1. Child-Pugh class score (subjects with hepatic impairment only);
2. AEs;
3. Interim medical history;
4. Weight;
5. Abbreviated PE ([Section 7.2.5](#));
6. Review of inclusion/exclusion criteria;
7. Screen for selected drugs of abuse, including an alcohol breath test for all subjects and, for matched-control healthy subjects only, including cotinine ([Appendix 2](#));
8. Twelve-lead ECG measured after the subject has been resting in the supine position for at least 10 minutes ([Section 7.2.4](#));

9. Vital signs (including oral temperature, respiratory rate, and supine BP and HR [measured after the subject has been supine for at least 5 minutes]) ([Section 7.2.3](#));
10. Clinical laboratory evaluations ([Section 7.2.2](#); clinical chemistry panel [fasted at least 8 hours], including CK, coagulation parameters, CBC, and UA; [Appendix 2](#));
11. How Do You Feel? inquiry and concomitant medication evaluations ([Section 7.2.1](#));
12. Serum pregnancy test for females only ([Appendix 2](#));
13. Compliance with concomitant medications and exclusionary restrictions ([Section 6](#)).

For subjects to continue their participation in the study, the inclusion/exclusion criteria must continue to be met at Day -1 (as appropriate; [Section 5](#)). In addition, continued compliance with concomitant medication and other restrictions will be verified.

The Covance Medical Monitor will review the medical history and all screening evaluations for potential subjects prior to enrollment. Prior to dosing, the Sponsor will provide written approval of subjects selected for enrollment by the Investigator.

Subjects who meet all the inclusion criteria and for whom none of the exclusion criteria apply will be eligible to be enrolled into the study. Safety evaluations may be repeated at the discretion of the Investigator (or designee), Covance Medical Monitor, or Sponsor.

#### **4.3. Inclusion Criteria**

Subjects who meet the following criteria at Screening and Check-in (Day -1), unless otherwise specified, may be included in the study:

##### **All subjects:**

1. Males, and females of nonchildbearing potential, between 18 and 65 years of age, inclusive, at Screening;
2. Within BMI range 18.5 to 40.0 kg/m^2, inclusive;
3. In good general health, except for additional specific inclusion criteria related to subjects with hepatic impairment, based on medical history, PE findings, vital signs, ECG, and clinical laboratory tests, as determined by the Investigator (or designee);
4. Females of nonchildbearing potential, defined as being permanently sterile (ie, due to hysterectomy, bilateral salpingectomy, bilateral oophorectomy, or confirmed tubal occlusion more than 6 months prior to study drug administration) or postmenopausal (defined as at least 12 months postcessation of menses without an alternative medical cause). Postmenopausal status will be confirmed with a screening serum follicle-stimulating hormone level within the site laboratory's range for postmenopausal status. All females must have a negative qualitative serum pregnancy test (serum human chorionic gonadotropin) at Screening and Check-in (Day -1);

5. Males who are capable of fathering a child must agree to use one of the following methods of contraception from the time of the dose administration through 6 months after dose administration:
  - Male sterilization, with documented confirmation of surgical success. Male subjects will be surgically sterile for at least 90 days prior to Check-in (Day -1). If documentation is not available, male subjects must follow one of the contraception methods below:
    - Male condom with spermicide, and
    - For a female partner of male study participant:
      - Intrauterine device (IUD) (hormonal IUD; eg, Mirena®). Copper IUDs are acceptable (eg, ParaGard®);
      - Established use of oral, implanted, transdermal, or hormonal method of contraception associated with inhibition of ovulation; or
      - Bilateral tubal ligation.

Males who practice true abstinence because of a lifestyle choice (ie, do not become abstinent just for the purpose of study participation) are exempt from contraceptive requirements. Periodic abstinence by a female partner (eg, calendar, ovulation, symptothermal, postovulation methods) and withdrawal are not acceptable methods of contraception. If a male subject is abstinent at the time of signing the ICF but becomes sexually active through EOS, he must agree to use contraception as described above.

For male subjects, sexual intercourse with female partners who are pregnant or breastfeeding should be avoided unless condoms with spermicide are used from the time of the study drug administration until 6 months after administration of study drug. Male subjects are required to refrain from donation of sperm from Check-in (Day -1) until 6 months after administration of study drug.

For subjects who are exclusively in same-sex relationships, contraceptive requirements do not apply.

6. Able to understand and provide written informed consent;
7. Able to comply with all study procedures, including the 11-night stay at the clinical site and Follow-up phone call;

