## SUMMARY OF AMENDED PROTOCOL CHANGES

The final protocol LOXO-RET-18022 Version 1, dated 15 October 2018, was amended for the following:

- To add the term End of Treatment (EOT) and define it as the time of clinic check-out. Where applicable, subject study restrictions were updated so the duration is through EOT or Early Termination (ET), rather than End of Study (EOS).
- To clarify that “Study Completion” applies to the clinical conduct of the study overall (last subject’s Follow-up phone call) and that “End of Study” applies to each subject for their individual Follow-up phone call (including for ET subjects), and to update instances where one of these terms was incorrectly used. Similarly, instances of “during the study” and “throughout the study” were updated to the appropriate term.
- To update inclusion criterion 5 regarding contraception, so that subjects must use a male condom with spermicide **and** a secondary method, instead of a male condom with spermicide **or** another listed method.
- To add an exclusion criterion prohibiting drugs that may prolong QT/QTc interval within 14 days prior to dose administration and through EOT or ET.
- To clarify exclusion criteria regarding abnormal laboratory values.
- To clarify exclusion criteria 13 and 14, and the concomitant medications and concomitant therapies sections, regarding medication restrictions and prohibited medications/substances with potential to interact or interfere with the study drug. As part of these changes, exclusion criterion 13 was split into separate restrictions for healthy subjects and hepatically impaired subjects, and the exclusion criteria were shifted and renumbered accordingly.
- To update exclusion criterion 39 regarding the restriction period for paracentesis from 56 days prior to Check-in (Day -1) to 30 days prior to Screening.
- To clarify restrictions on consumption of fruit juices such that juices other than grapefruit and orange are not allowed within 72 hours prior to dose administration and through EOT or ET.
- To clarify that there are no restrictions around water consumption during the study.
- To clarify when adverse events (AEs) should be classified as medical history or as AEs.
- To clarify that AEs occurring in a subject between EOT or ET and EOS should only be reported if the event is a serious adverse event or is considered related to study drug.

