The schematic of the study design is displayed in [Figure 1](#). The start of the study is defined as the date the first subject who is enrolled in the study signs an Informed Consent Form (ICF). Note that enrolled subjects are defined as those subjects who are assigned a dose of study drug; this definition excludes screen failure subjects.

Subjects will be confined at the clinical site from the time of Check-in (Day -1) until EOT on Day 11 upon completion of all PK and safety assessments or ET if the Subject discontinues. A Follow-up phone call will occur 7 days ( $\pm$  2 days) after EOT or ET.

On the morning of Day 1, after at least a 2-hour fast, a single oral dose of 160 mg LOXO-292 will be administered with 240 mL water. No food will be allowed for up to 1 hour postdose. Glucose tablets may be administered as needed for treatment of hypoglycemia. For instructions regarding food and water intake, please refer to [Section 6.2](#).

**Figure 1** Study Design Schematic

ICF = Informed Consent Form; PK = pharmacokinetic.

Note: Single oral dose of LOXO-292 at 160 mg administered orally after at least a 2-hour fast.

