##### **All subjects:**

1. Males, and females of nonchildbearing potential, between 18 and 65 years of age, inclusive, at Screening;
2. Within BMI range 18.5 to 40.0 kg/m^2, inclusive;
3. In good general health, except for additional specific inclusion criteria related to subjects with hepatic impairment, based on medical history, PE findings, vital signs, ECG, and clinical laboratory tests, as determined by the Investigator (or designee);
4. Females of nonchildbearing potential, defined as being permanently sterile (ie, due to hysterectomy, bilateral salpingectomy, bilateral oophorectomy, or confirmed tubal occlusion more than 6 months prior to study drug administration) or postmenopausal (defined as at least 12 months postcessation of menses without an alternative medical cause). Postmenopausal status will be confirmed with a screening serum follicle-stimulating hormone level within the site laboratory's range for postmenopausal status. All females must have a negative qualitative serum pregnancy test (serum human chorionic gonadotropin) at Screening and Check-in (Day -1);
5. Males who are capable of fathering a child must agree to use one of the following methods of contraception from the time of the dose administration through 6 months after dose administration:

- Male sterilization, with documented confirmation of surgical success. Male subjects will be surgically sterile for at least 90 days prior to Check-in (Day -1). If documentation is not available, male subjects must follow one of the contraception methods below:
  - Male condom with spermicide, or
  - For a female partner of male study participant:
    - Intrauterine device (IUD) (hormonal IUD; eg, Mirena®). Copper IUDs are acceptable (eg, ParaGard®);
    - Established use of oral, implanted, transdermal, or hormonal method of contraception associated with inhibition of ovulation; or
    - Bilateral tubal ligation.

Males who practice true abstinence because of a lifestyle choice (ie, do not become abstinent just for the purpose of study participation) are exempt from contraceptive requirements. Periodic abstinence by a female partner (eg, calendar, ovulation, symptothermal, postovulation methods) and withdrawal are not acceptable methods of contraception. If a male subject is abstinent at the time of signing the ICF but becomes sexually active during the study, he must agree to use contraception as described above.

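### Criterion 5 ties an abstinent man's duty to start contraception to activity up to EOS (Day 16 to 20), although the male contraception period runs to 6 months (minor wording point)

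*Protocol*

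**What the plan says.** Criterion 5 in Section 4.3 of the current protocol (Version 2) has four parts that bear on this point.

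- **General rule.** Men capable of fathering a child must use contraception "from the time of the dose administration through 6 months after dose administration".
- **Exemption.** "Males who practice true abstinence because of a lifestyle choice" are exempt from the contraceptive requirements. No end date is given.
- **End of abstinence.** "If a male subject is abstinent at the time of signing the ICF but becomes sexually active through EOS, he must agree to use contraception". The methods are those listed earlier in the criterion.
- **Neighbouring restrictions.** "Male subjects are required to refrain from donation of sperm from Check-in (Day -1) until 6 months after administration of study drug". Intercourse with a pregnant or breastfeeding partner is to be avoided "unless condoms with spermicide are used from the time of the study drug administration until 6 months after administration of study drug".

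Appendix 5, footnote s, defines EOS as the follow-up call 7 (±2) days after EOT or ET. Under Section 3.1, subjects stay in the clinic "until EOT on Day 11 upon completion of all PK and safety assessments", unless they discontinue earlier. None of the letters of change supplied with the protocol alters the abstinence sentence.

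**The concern.** The criterion uses two different end points for one obligation. The contraception period, the sperm-donation ban and the condom rule all run to 6 months. The sentence that says when an abstinent man must start contraception stops at EOS, less than three weeks after the dose. Because that sentence deals with exactly this event and carries an express end point, site staff counselling a subject could reasonably conclude that a man who first becomes active after the call owes nothing further.

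What is at stake is partner protection, for men first active between EOS and 6 months with a female partner who is neither pregnant nor breastfeeding. A man who becomes active by EOS is covered to 6 months.

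The likely origin is visible. Version 1 applied the sentence to a man who "becomes sexually active during the study, he must agree to use contraception as described above". The Summary of Amended Protocol Changes says that instances of that study-period phrase "were updated to the appropriate term". It states no intention to shorten the duty, so the EOS limit looks like a by-product of the terminology clean-up. This is an inference about origin; the concern itself rests on the current text.

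**Working it through.** There is no plan figure to reproduce. The check is calendar arithmetic on the protocol's own time points.

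**Inputs**

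- Day 11 is 240 hours postdose (Appendix 5, footnote j), so Day *d* is *d* − 1 days after the dose and EOT is 10 days postdose.
- EOS is EOT + 7 ± 2 days (Appendix 5, footnote s).
- The contraception period is 6 months from dosing (criterion 5). The protocol does not convert this to days. I take 182 days, with a range of 181 to 184 depending on the calendar date of dosing.
- Half-life is about 24 hours after a single dose (Section 1.3).
- Planned enrolment is up to 24 impaired and up to 16 healthy subjects (Synopsis).

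**Timing of EOS for a subject who completes Day 11**

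- Earliest: 10 + 5 = 15 days postdose (Day 16).
- Latest: 10 + 9 = 19 days postdose (Day 20).

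**Interval between EOS and the end of the contraception period**

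| Length of 6 months | Shortest interval | Longest interval |
|---|---|---|
| 182 days | 182 − 19 = 163 days | 182 − 15 = 167 days |
| 181 to 184 days | 181 − 19 = 162 days | 184 − 15 = 169 days |

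For a subject who terminates early, EOS falls 5 to 9 days after release, so the interval is longer.

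**What the sentence does cover.** A completer is confined until Day 11. After release, the EOS limit adds only 5 to 9 days in which first activity is expressly addressed.

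**Context for severity**

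- Subjects: 24 + 16 = 40 at most, both sexes together, before any replacements. The number of men who would be abstinent at consent and first active after EOS is not known.
- Half-lives elapsed by EOS: 15 × 24/24 = 15 to 19 × 24/24 = 19. If impairment doubled the half-life to 48 hours (an assumption), 15 × 24/48 = 7.5 to 19 × 24/48 = 9.5.

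The 163 to 167 days is the width of the interval in which the duty is unclear. It is not time that any man is known to be unprotected.

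**The case against.** The strongest reply is that the criterion already supplies the rule. The general sentence binds every man capable of fathering a child for 6 months, and the exemption is narrow and in the present tense. A man who becomes active no longer meets it, so the 6-month duty applies again. Nothing says contraception is unnecessary after EOS, and the neighbouring restrictions point to 6 months. This reading is plausible and probably what the sponsor intends, which is why the duty is called uncertain and not absent. It leaves the EOS end point with no work to do, however, and a reader who gives it meaning reaches the opposite answer.

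A second reply is that EOS is the last scheduled contact, so it is the last planned occasion to obtain a new agreement. But other men agree at entry to a duty that runs well past EOS, and an abstinent man could give a conditional agreement in the same way.

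Third, Version 1 did not say 6 months in this sentence either. That is correct: the amendment did not displace a 6-month trigger. It bears on how the wording arose, not on what it now says.

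Fourth, the practical effect depends on the consent form, which was not available. This stands. Under Appendix 4 subjects receive the ICF, and if it states 6 months the gap does not reach them. Section 1.2 also reports that the drug was not mutagenic in the bacterial assay and not genotoxic in two in vitro assays. This does not settle reproductive risk, but it supports a low severity.

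Men are also told to report a partner's pregnancy at once (Appendix 1, Section 1.3). That detects a pregnancy; it does not prevent one.

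**Conclusion.** The point holds as a minor wording defect. The one sentence on abstinence ending conflicts with the criterion's own 6-month period, and it leaves the duty unclear for a man first active in the 163 to 167 days after EOS (162 to 169 days across the possible lengths of 6 months).

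This rests on three things: the subject completes Day 11, 6 months is about 182 days, and the site works from the protocol text. It does not establish that any partner would be exposed. Few men are likely to be affected, although the documents give no figure. EOS is about 15 to 19 half-lives after a single dose. The PK and safety analyses are unaffected.

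**What to change.** In criterion 5, replace *through EOS* in the abstinence sentence with *within 6 months after dose administration*, so that the trigger matches the contraception period. Check the consent form and align its wording if it differs. A reminder at the existing EOS call is optional.

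The cost is one phrase in the protocol and, if needed, one in the consent form. It adds no visits, tests or subjects. The sponsor has already used letters of change for comparable corrections, such as adding tubal ligation to the criterion on female sterilisation.
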